6.5.4. Analysis of Dose Proportionality for PK parameters

Dose proportionality will be evaluated for healthy subjects in Part A who were administered VIR-3434 SC. Dose proportionality may also be evaluated for participants in Part B, C, and D. PK parameters from subjects with dosing deviation will be excluded from the analysis.

To assess dose proportionality, the natural log transformed PK parameters, including AUC_{inf} (AUC_{last} and/or AUC_{0-t} will be used if AUC_{inf} is poorly estimated) and C_{max} , will be analyzed using power model [1], with VIR-3434 log transformed dose level as the independent variable, in form of $\ln(y) = \beta_0 + \beta_1 * \ln(\text{VIR-3434 dose})$, where y = the PK parameter of interest.

Dose proportionality is concluded if 90% CI for the β_1 falls within the critical interval of (0.7, 1.43), which is less than 30% difference between doses for a given PK parameter.

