5.3.1. Part A Study Drug Dosing, Study Progression, and Dose Escalation

Overview: There are 3 planned cohorts in Part A: 90 mg SC (Cohort 1a), up to 300 mg SC (Cohort 2a), and up to 900 mg SC (Cohort 3a; Table 3). The SRC will review available laboratory and clinical safety data through 2 weeks post-dose from the last available subject in the current Part A cohort prior to permitting dosing in subsequent cohorts. While all of the SC cohorts (Cohort 1a, 2a, and 3a) in Part A are planned to be enrolled sequentially, cohorts may be enrolled in parallel if the additional cohort(s) is examining a dose level which is at or below a dose level that has previously been found to have an acceptable safety and tolerability profile in a prior cohort in Part A.

Optional Cohorts: Optional IV cohorts (Cohorts 4a and 5a) may be enrolled and dosed based on SRC review of available safety and tolerability data through at least 2 weeks after the last available subject is dosed within Cohort 3a. Enrollment of Cohorts 4a and 5a will be according to the same Part A eligibility criteria as the planned Part A cohorts.

Table 3: Part A Cohort Overview

Study Part	Cohort	Route	Dose Level	Active:Placebo
A	1a	SC	90 mg	6:2
A	2a	SC	up to 300 mg	6:2
A	3a	SC	up to 900 mg	6:2
A	4a (optional)	IV	up to 900 mg	6:2
A	5a (optional)	IV	up to 3,000 mg	6:2

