3. STUDY DESIGN

3.1. Overall Design

VIR-3434-1002 is a Phase 1, randomized, double-blind, placebo-controlled, single ascending dose (SAD) study to evaluate the safety, tolerability, PK, and antiviral activity of VIR-3434 administered by subcutaneous (SC) injection or intravenous (IV) infusion in healthy adult subjects and adult subjects with chronic HBV infection without cirrhosis.

The schema of the study design schema is provided as shown in below Figure 1:

Figure 1: Study Schema

[figure not shown]

Approximately up to 144 participants are planned to be randomized in Part A and Part B, C, and D.

- **Part A:** approximately 8 participants will be randomized (3:1) to either 1 of up to 5 planned dose-sequential cohorts (VIR-3434) or placebo cohort. The healthy participants will be discharged on Day 2 and will be followed up to 24 weeks, as shown in Figure 2.
- **Part B, C, and D:** approximately 8 participants will be randomized (3:1) to either 1 of VIR-3434 dose-sequential cohorts (up to 7/3/3 planned cohorts for Part B/C/D accordingly) or placebo cohort in Part B, C, and D respectively. Participants will be discharged after all study assessments completed on Day 1 and will be followed up to 8 weeks, as shown in Figure 3.

For participants with > 2-fold HBsAg reduction from baseline at Week 8 will be followed for additional 32 weeks up to Week 40 or until the reduction is < 2-fold relative to baseline at 2 consecutive collections, whichever occurs first.

Figure 2: Part A: SAD in healthy adults

* subjects discharge will occur after all assessments are completed on Day 2

Figure 3: Parts B, C, and D: SAD for adults with chronic HBV infection without cirrhosis

The dose escalation of study intervention and the corresponding cohorts with the enrollment status for Part A and Part B, C, and D are showed in below Table 1 and Table 2 respectively:

Table 1: Dose Escalation Cohorts in Part A

Study Part	Cohort	Route	Dose Level (VIR-3434)	Enrolled
A	1a	SC	90 mg	Yes
A	2a	SC	300 mg	Yes
A	3a	SC	900 mg	Yes
A	4a (optional)	IV	900 mg	Yes
A	5a (optional)	IV	3,000 mg	Yes

Table 2: Dose Escalation Cohorts in Part B, C, and D

Study Part	Cohort	Route	Dose Level (VIR-3434)	Enrolled
B	1b	SC	6 mg	Yes
B	2b	SC	18 mg	Yes
B	3b	SC	75 mg	Yes
B	4b	SC	300 mg	Yes
B	5b	SC	up to 900 mg	No
B	6b (optional)	SC	up to 900 mg	No

Study Part	Cohort	Route	Dose Level (VIR-3434)	Enrolled
B	7b (optional)	SC	up to 900 mg	No
C	1c (optional)	SC	18 mg	Yes
C	2c (optional)	SC	75 mg	Yes

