4. STATISTICAL HYPOTHESES

There are no formal statistical hypotheses planned for this study.

This study is exploratory in nature. No multiplicity adjustment will be made.

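### The dose-proportionality limits (0.7, 1.43) are placed on the power-model slope but described as a 30% difference; over 90–900 mg SC they allow dose-normalised ratios from 0.50 to 2.69

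*SAP*

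**What the plan says.** SAP 6.5.4 commits to one analysis: "Dose proportionality will be evaluated for healthy subjects in Part A who were administered VIR-3434 SC". It fits a power model, ln(y) = b0 + b1·ln(dose), "with VIR-3434 log transformed dose level as the independent variable", to AUCinf (or a substitute AUC if AUCinf is poorly estimated) and Cmax. The decision rule begins "Dose proportionality is concluded if 90% CI for the" slope and requires that interval to be one that "falls within the critical interval of (0.7, 1.43), which is less than 30% difference between doses for a given PK parameter". The section gives no dose ratio and no conversion from ratio limits to slope limits.

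SAP Table 1 (section 3.1) marks the 90, 300 and 900 mg SC cohorts as enrolled. Protocol Table 3 (section 5.3.1) plans six active subjects in each. For the other Parts the analysis is optional: "Dose proportionality may also be evaluated for participants in Part B, C, and D". The protocol contains no dose-proportionality criterion of its own.

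**The concern.** A power-model slope has no fixed meaning in percent. The same slope implies a small departure from proportionality over a 2-fold dose range and a large one over a 10-fold range. Limits of 0.7 and 1.43 are natural for a ratio of dose-normalised exposures. Placed on the slope, they mean something different, and what they mean depends on the dose range.

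This is the one place where the SAP draws a conclusion from a confidence interval. Followed literally, the report could call exposure dose proportional to within 30% when the same confidence interval, converted to the exposure scale, shows a larger departure.

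**Working it through.** **Inputs.** Model, limits and 90% level: SAP 6.5.4. Doses 90, 300 and 900 mg SC: SAP Table 1. Six active per dose, 18 in total: Protocol Table 3. Between-subject CV: not in the documents, so 25, 35 and 50% are assumed. The conversion in steps 1 to 3 needs no CV.

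**1. The plan's own figure.** 1/0.7 = 1.4286, so (0.7, 1.43) is a reciprocal ratio pair. From the model, y/dose is proportional to dose^(b1−1), so the dose-normalised ratio between two doses r-fold apart is r^(b1−1). Setting b1 to each limit:

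| Comparison | r | r^(0.7−1) | r^(1.43−1) |
|---|---|---|---|
| 90 to 900 mg | 10 | 0.501 | 2.692 |
| 90 to 300 mg | 3.33 | 0.697 | 1.678 |
| 300 to 900 mg | 3 | 0.719 | 1.604 |

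The 30% description is not reproduced over the full range. For adjacent doses it is reproduced on the lower side only.

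**2. When would the description be true?** The lower edge equals 0.7 at r = 0.7^(−1/0.3) = 3.28. The upper edge equals 1.43 at r = 1.43^(1/0.43) = 2.30. Both edges stay within 0.7–1.43 only for r ≤ 2.30. No two enrolled SC doses within a Part are closer than 3-fold.

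**3. A result that passes and contradicts the description.** A slope CI of 1.16 to 1.42 lies inside (0.7, 1.43). Over 90–900 mg it converts to 10^0.16 = 1.45 and 10^0.42 = 2.63, a ratio interval wholly above 1.43.

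**4. How often departures pass.** The sum of squares of ln(dose) about its mean is 6 × 2.653 = 15.92. The residual SD is √ln(1 + CV²), and the slope SE is that SD divided by √15.92: 0.062, 0.085 and 0.118 at CV 25, 35 and 50%. With t(16; 0.95) = 1.746, the 90% half-widths are 0.108, 0.149 and 0.207. One million simulated trials give these chances of concluding proportionality under the SAP rule:

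| True slope | True 900 vs 90 mg ratio | CV 25% | CV 35% | CV 50% |
|---|---|---|---|---|
| 0.70 | 0.50 | 5% | 5% | 5% |
| 0.845 | 0.70 | 73% | 49% | 32% |
| 1.00 | 1.00 | 99.9% | 96% | 75% |
| 1.155 | 1.43 | 99.6% | 92.5% | 70% |
| 1.25 | 1.78 | 87% | 65% | 42% |
| 1.43 | 2.69 | 5% | 5% | 5% |

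The whole CI must lie inside the limits, so a true slope at an edge passes only about 5% of the time; 0.50 and 2.69 are edges, not departures that usually pass. A rule that truly had a 0.70–1.43 tolerance over this range would pass the 0.845 and 1.155 rows at most 5% of the time.

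The true ratio that passes half the time is 2.11, 1.92 and 1.68 on the upper side and 0.64, 0.70 and 0.80 on the lower side. Once the CV is 35% or more, the excess leniency is therefore mainly upward.

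**5. Slope limits that would match the description.** Over r = 10: 1 + ln(0.7)/ln(10) = 0.845 and 1 − ln(0.7)/ln(10) = 1.155.

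**The case against.** - **Adjacent doses.** The SAP does not say that the comparison is highest against lowest. With adjacent doses the lower edge (0.70–0.72) is essentially what the SAP claims. This stands for the lower side; the upper edge, 1.60–1.68, still misses.
- **The rule is defensible and only its description is wrong.** The width of tolerance is the sponsor's choice, and at a true slope of 1 the rule concludes correctly in 99.9, 96 and 75% of trials at CV 25, 35 and 50%. This stands, and it is why the preferred fix leaves the rule alone.
- **Upward departures are not expected in Part A.** Protocol 2.3.2 says the antibody has no endogenous target in healthy subjects and predicts human PK from a linear model. So slopes of 1.155 to 1.25 test the rule and are not forecasts. That does not make the stated tolerance correct.
- **An outright contradiction is often rare.** At a true slope of 1.25, the rule passes with the whole ratio CI above 1.43 in 31, 5 and 0.2% of trials at CV 25, 35 and 50%. It is common only when variability is low.
- **Eighteen is a planned maximum.** SAP 6.5.4 excludes subjects with dosing deviations. Fewer subjects widen the CI and lower the pass rates. The edges 0.50 and 2.69 do not change.
- **Little depends on it.** SAP section 4 says "This study is exploratory in nature", PK is secondary, and geometric means are reported by cohort (SAP 6.5.3). This limits the consequence, but the geometric means do not correct the stated verdict.

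**Conclusion.** The concern holds. The 30% description does not follow from slope limits of (0.7, 1.43). Over the committed 10-fold range those limits correspond to dose-normalised ratios of 0.50 and 2.69, and on the most favourable reading the upper edge is still 1.60–1.68. These figures need only the SAP's model and its dose table. The pass rates rest further on 18 evaluable subjects, log-normal data and the assumed CVs.

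It should be fixed, but its reach is modest. No safety or antiviral analysis depends on it, and the documents tie no dosing decision to it. The optional analyses in Parts B to D add nothing to the seriousness.

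**What to change.** In SAP 6.5.4, report b1 and r^(b1−1) with 90% CIs, where r is the highest dose analysed divided by the lowest, and make the criterion and its description agree.

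**Option 1 (preferred).** Keep the decision rule, delete the clause about a 30% difference, and state the tolerance the rule allows: 0.50 to 2.69 over 90–900 mg SC. Cost: one sentence and one extra reported quantity, with no new data.

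**Option 2 (only if the 30% claim is to be kept).** Require the 90% CI of r^(b1−1) to lie within 0.70–1.43, which for Part A SC means slope limits of 0.845 to 1.155. Cost: many more inconclusive results. At a true slope of 1, the chance of concluding proportionality falls from 99.9, 96 and 75% to about 55, 14 and 1% at CV 25, 35 and 50%.

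If the optional analysis is done in Parts B to D, state r and the implied tolerance for each Part. With the doses enrolled in SAP Table 2, the present limits would give 0.31 to 5.38 in Part B (6–300 mg, r = 50), 0.43 to 3.35 in Part C (18–300 mg, r = 16.7) and 0.66 to 1.815 in Part D (75–300 mg, r = 4).

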6.6. Immunogenicity Analysis

All immunogenicity analyses described in this section will be based on the Immunogenicity Analysis Set and presented by treatment cohort, treatment total, and placebo, for Part A and Part B, C, and D separately, unless specified otherwise.

6.6.1. Definition of Variables

The immunogenicity analysis will be analyzed through the following antidrug antibodies (ADA) to VIR-3434 variables:

- Binding ADA: binding ADA is defined as any antibodies (neutralizing and non-neutralizing) binding biologic drug, which is determined by the positive results from both screening and confirmed test using an *in vitro* test method. Any positive screening result followed by a confirmed negative result, will be treated as negative response.
- Titers: the presence and quasi-quantitative expression of the level of ADA, which is determined by serially diluting the serum fraction of blood and assaying (testing) each dilution for the antibody of interest
- Treatment-induced ADA: is defined as a baseline sample negative for ADA (or missing) and a post-baseline sample confirmed positive for ADA.
- Treatment-boosted ADA: is defined as pre-existing ADA (confirmed positive at baseline) that is boosted to >4x baseline ADA titer at any post-baseline measures.
- Treatment-unaffected ADA: is defined as pre-existing ADA (confirmed positive at baseline) that is changed to native or increased to $\leq 4x$ baseline ADA titer at all post-baseline measures.
- Transient ADA: ADA is defined as transient if the last ADA result for a participant is negative but there is treatment-induced ADA at only one time point (excluding the last non-missing result) or there are ≥ 2 samples with treatment-induced ADA with fewer than 16 weeks between the first and last samples that are positive for ADA (irrespective of negative samples in between).
- Persistent ADA: ADA is defined as persistent if there are ≥ 2 samples at different timepoints with treatment-induced ADA with 16 or more weeks between the first and the last samples that are positive for ADA or there is treatment-induced ADA at the final timepoint.

6.6.2. Analysis Methods

The incidence rate of participants who had samples of negative, screened positive, and confirmed positive for binding ADA to VIR-3434 will be summarized using frequency counts and percentage at baseline and each post-baseline visit up to Week 24 (Part A) or Week 8 (Part B, C, and D). Titers for participants confirmed positive for ADA to VIR-3434 will be summarized descriptively (n, median, min, max).

A summary table of immunogenicity results will be provided including the number of study participants with:

- Any ADA result
- Both baseline and post-baseline ADA
- Any baseline ADA
- Any post-baseline ADA

The number and percentage of participants (based on the participants with any post-baseline ADA) in each of the following ADA type category will be provided. In addition, titers for participants with ADA to VIR-3434 will also be summarized descriptively (n, median, min, max) for ADA types, including treatment-induced ADA, treatment-boosted ADA, and treatment-unaffected ADA.

- Treatment-emergent ADA (treatment-induced or treatment-boosted)
- Treatment-induced ADA
- Treatment-boosted ADA
- Treatment-unaffected ADA

For transient or persistent ADA to VIR-3434, the number and percentage of participants (based on the participants with any post-baseline ADA) will be summarized. Titers for participants with transient or persistent ADA to VIR-3434 will also be summarized descriptively (n, median, min, max).

An individual participant listing will be provided by subject ID, visit in chronological order.

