Parts B, C, and D: All subjects will be followed for 8 weeks after study drug administration. Subjects with > 2-fold HBsAg reduction at Week 8 will undergo extended follow-up for up to 40 weeks total or until the reduction in HBsAg is < 2-fold relative to baseline at 2 consecutive collections, whichever occurs first. The extended follow-up may be discontinued at the Sponsor's discretion based on emerging data.

Study Design

This study is designed to evaluate the safety, tolerability, PK, and antiviral activity of VIR-3434.

A Safety Review Committee (SRC) will perform ongoing reviews of safety, tolerability, and antiviral activity data (Parts B and C only) at specified timepoints based on available data collected throughout the study. While the primary data that will be reviewed by the SRC for dose escalations and enrollment

of optional cohorts is listed throughout the protocol, additional relevant data from other cohorts may also be reviewed by the SRC to inform decisions. Details are provided in the SRC charter.

The study will be conducted in 4 Parts:

- **Part A:** Randomized, double-blind, placebo-controlled, single ascending dose (SAD) study of VIR-3434 administered via subcutaneous (SC) injection or intravenous (IV) infusion to healthy adult subjects
- **Part B:** Randomized, double-blind, placebo-controlled, SAD study of VIR-3434 administered via SC injection to adult subjects with chronic HBV infection without cirrhosis who are on NRTI therapy, are HBeAg-negative, and have HBsAg < 3,000 IU/mL
- **Part C:** Optional, randomized, double-blind, placebo-controlled, SAD study of VIR-3434 administered via SC injection to adult subjects with chronic HBV infection without cirrhosis who are on NRTI therapy, are HBeAg-negative or HBeAg positive, and who have HBsAg \geq 3,000 IU/mL
- **Part D:** Optional, randomized, double-blind, placebo-controlled, SAD study of VIR-3434 administered via SC injection to adult subjects with chronic HBV infection without cirrhosis who are not on NRTI therapy, have HBV DNA \geq 1,000 IU/mL, are HBeAg-negative or HBeAg positive, and have any HBsAg level

Part A

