Results from a non-GLP PK study in cynomolgus monkeys (PK-3434-0109) was used to develop a linear two-compartment PK model which was further scaled to human using allometry. Human VIR-3434 serum clearance and volume of distribution were predicted to be approximately 65.7 mL/day and 2.43 L, respectively, in the central compartment and 612.7 mL/day and 2.85 L, respectively, in the peripheral compartment. Based on these estimations, terminal elimination half-life of VIR-3434 in humans was predicted to be approximately 58 days. These parameters were used to simulate human PK profiles over the proposed Part A dose range of 90 to 900 mg administered by SC injection and 900 mg and 3,000 mg administered by IV infusion. Additional information is provided in the Investigator’s Brochure.

Table 1: Part A Dose Escalation Plan

Study Part	Cohort	Active:Placebo	Dose (Route)	Frequency of Administration
A	1a	6:2	90 mg (SC)	Once
	2a	6:2	Up to 300 mg (SC)	Once
	3a	6:2	Up to 900 mg (SC)	Once
	4a (Optional)	6:2	Up to 900 mg (IV)	Once
	5a (Optional)	6:2	Up to 3,000 mg (IV)	Once

IV = intravenous; SC = subcutaneous.

Part B: Single Ascending Dose Study in Subjects with Chronic HBV Infection

In Part B, subjects with chronic HBV infection will receive a single dose of study drug. The presence of the therapeutic target of VIR-3434, HBsAg, in subjects with chronic HBV infection alters the potential risks of VIR-3434 administration. Potential risks include immune complex disease due to the formation of antigen-antibody complexes and hepatotoxicity due to elimination of infected hepatocytes via ADCC/ADCP and/or a “vaccinal effect”. To minimize risks to subjects, Part B will be conducted in subjects who are on NRTIs and have HBV DNA < 100 IU/mL at screening, and who have good hepatic reserve and low levels of hepatic inflammation, as determined by lack of significant fibrosis/cirrhosis and ALT $\leq 2 \times$ ULN.

Available non-clinical toxicology and PK/PD data, as well as experience with molecules having similar characteristics, were taken into account when selecting the starting dose and dose escalation scheme for VIR-3434 in subjects with chronic HBV infection. The proposed starting dose of 6 mg (approximately 0.1 mg/kg) is supported by the following rationale:

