Adult subjects with HBeAg-negative chronic HBV infection without cirrhosis and with HBsAg < 3,000 IU/mL on NRTI therapy for ≥ 2 months will be enrolled in 1 of 7 cohorts (5 planned, 2 optional) in Part B. Subject screening will occur no more than 6 weeks prior to the Day 1 visit. Subjects may be admitted into the clinical investigative site on Day -1 or 1. Prior to study drug administration on Day 1, subject eligibility will be confirmed. Any changes to medical history will also be evaluated and recorded. Eligible subjects in each cohort will be randomized to receive VIR-3434 or placebo within 48 hours prior to study drug administration on Day 1.

At the start of each cohort, 2 sentinel subjects will be randomized 1:1 to VIR-3434 or placebo. These subjects will be dosed and monitored through at least 72 hours post-dose; if the investigator(s) have no safety concerns, the remainder of the subjects in the same cohort will be dosed. Vital signs, symptom-directed physical examination(s), and AEs will be reviewed by the investigator prior to dosing any additional subjects. The remaining subjects in the cohort will be randomized 5:1 to receive a single dose of VIR-3434 or placebo. All subjects will be closely

monitored following dose administration. In the event of an acute immune reaction (such as anaphylaxis or cytokine release syndrome) recommended therapeutic and supportive measures can be found in [Appendix 8](#).

Patients must be monitored through at least 6 hours post-dose prior to discharge. Subjects will be discharged after all study assessments are performed on Day 1. All subjects will return to the clinical investigative site per the schedule of assessments ([Appendix 3](#)) through the final required follow-up day (Week 8). In the event of suspected immune complex disease, recommended therapeutic and supportive measures can be found in [Appendix 8](#). Subjects with > 2-fold HBsAg reduction at Week 8 will be followed for an additional 32 weeks or until the reduction in HBsAg is < 2-fold relative to baseline at 2 consecutive collections, whichever occurs first. During this extended follow-up period, subjects will return to the clinical investigative site for assessments per the schedule of assessments ([Appendix 3](#)). Extended follow-up may be discontinued for any subject at Sponsor's discretion based on emerging data.

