10.7. Immunogenicity Analysis

For all study parts, immunogenicity data will be listed and summarized using descriptive statistics, including rates, titers, and neutralization data, as applicable.

Correlations between immunogenicity data and safety, efficacy, and PK data will be explored. These analyses may include graphical plots, tabular summaries, and various linear and/or nonlinear analyses. Details of immunogenicity analyses will be provided in the Statistical Analysis Plan

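### In Parts B–D the ADA-type and transient/persistent summaries have no Week 8 limit, although planned ADA sampling after Week 8 depends on HBsAg response

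*SAP*

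**What the plan says.** **Who is sampled.** Protocol Appendix 3 schedules ADA samples in Parts B–D on Day 1 and at Weeks 2, 4 and 8, then at Weeks 12, 16, 24, 32 and 40 of extended follow-up. The synopsis sets the required period: "Parts B, C, and D: All subjects will be followed for 8 weeks after study drug administration". Entry to the extension depends on antiviral response (Protocol 5.1.2, repeated in 5.1.3 and 5.1.4): "Subjects with > 2-fold HBsAg reduction at Week 8 will be followed for an additional 32 weeks". It ends at Week 40, when the reduction falls below 2-fold at two collections in a row, or when the Sponsor stops it.

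**What is tabulated.** SAP 6.6.2 gives by-visit ADA incidence for Parts B–D only to Week 8. The next table carries no such limit: "The number and percentage of participants (based on the participants with any post-baseline ADA) in each of the following ADA type category will be provided". The transient/persistent summary has none either. In SAP 6.6.1, treatment-induced ADA "is defined as a baseline sample negative for ADA (or missing) and a post-baseline sample confirmed positive for ADA"; boosting likewise counts any post-baseline measure. SAP Appendix 2 maps immunogenicity results to analysis visits up to extended Week 40, so late samples do reach these derivations. SAP 6.6 presents results by treatment cohort, treatment total and placebo.

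**What is to be correlated.** Protocol 10.7 adds: "Correlations between immunogenicity data and safety, efficacy, and PK data will be explored". It leaves the details to the SAP.

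**The concern.** Immunogenicity is a secondary objective, and ADA incidence a secondary endpoint, in Parts B–D. A category defined by any positive sample fills up as samples are added. Here the number of planned samples is set by HBsAg response, itself a secondary endpoint. A cohort with more sustained HBsAg reduction gets more chances to show treatment-induced or boosted ADA, and fewer of its subjects with pre-existing ADA can stay in the unaffected class. Placebo subjects, who supply the background rate, would mostly leave at Week 8.

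A reader comparing cohorts with each other or with placebo could take a difference in observation time for a difference in immunogenicity. An ADA–efficacy correlation built on the same categories would be pushed towards linking ADA with better response. The persistence label has a related problem, because its duration criterion is longer than the required follow-up.

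**Working it through.** **1. The plan's own figure.** Protocol 2.3.2 states that "terminal elimination half-life of VIR-3434 in humans was predicted to be approximately 58 days". The central-compartment inputs are given as follows: "Human VIR-3434 serum clearance and volume of distribution were predicted to be approximately 65.7 mL/day and 2.43 L, respectively, in the central compartment". For the second compartment the protocol lists a volume of 2.85 L and a clearance of 612.7 mL/day, which I read as inter-compartmental.
- k10 = 0.0657/2.43 = 0.0270, k12 = 0.6127/2.43 = 0.2521, k21 = 0.6127/2.85 = 0.2150 per day; s = their sum = 0.4942.
- β = [s − √(s² − 4·k10·k21)]/2 = 0.01206 per day; ln 2/β = 57.5 days, which agrees with the stated value.
- Week 8 (56 days) is 56/57.5 = 0.97 of a predicted half-life. This only places Week 8 on the exposure curve; the conclusion does not rest on it.

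**2. Planned post-baseline ADA samples.**
- Leaves at Week 8: Weeks 2, 4, 8 = 3.
- Enters the extension and loses response at once: the two consecutive collections are Weeks 12 and 16, so 3 + 2 = 5.
- Followed to Week 40: 3 + 5 = 8.

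**3. Effect on an any-time incidence.** The documents give no ADA rates, so these are assumed. Let p be the proportion positive by Week 8, q the proportion of the remainder first positive afterwards, and e the share of subjects sampled after Week 8. True risk is the same for everyone.

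Observed incidence = p + (1 − p)·q·e

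| p | q | e = 0 | e = 0.5 | e = 1 |
|---|---|---|---|---|
| 5% | 5% | 5% | 7.4% | 9.8% |
| 5% | 10% | 5% | 9.8% | 14.5% |
| 5% | 20% | 5% | 14.5% | 24% |

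For example, 0.05 + 0.95 × 0.20 × 1 = 0.24. With p = 0 and q = 5, 10 or 20%, the contrast between e = 0 and e = 1 is 0% against 5, 10 or 20%. With p = 10% it is 10% against 14.5, 19 or 28%. In a cohort with 6 active subjects, p = 5% gives 6 × 0.05 = 0.3 expected positives at e = 0 and 6 × 0.0975 = 0.6 to 6 × 0.24 = 1.4 at e = 1.

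Taking e near 0 for placebo is also an assumption. For Parts B and C it fits Protocol 2.3.2, which gives 0.3 log10 (10^0.3 ≈ 2-fold) as the mean HBsAg decline over 48 weeks of NRTI therapy.

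**4. Persistence (SAP 6.6.1).** One route needs 16 weeks or more between first and last positive samples; the other needs a positive at the final timepoint.
- Week 2 to Week 8: (57 − 15)/7 = 6.0 weeks; at the edges of the visit windows, (64 − 13)/7 = 7.3.
- Week 2 to Week 16: (113 − 15)/7 = 14.0 weeks; at the edges, (120 − 13)/7 = 15.3.
- Week 2 to Week 24: (169 − 15)/7 = 22.0 weeks.

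The duration route is closed at Week 8 and at Week 16, the earliest response-based exit. It opens only at Week 24. A subject leaving at Week 8 can be persistent only by being positive at the last sample. The same ADA course can therefore get two labels: positive only at Week 8 is persistent for a subject who leaves then, but transient for one whose Week 12 and later samples are negative.

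**5. After a common cut.** With samples through Week 8 only, everyone has 3 planned post-baseline samples. Step 3 then returns p in every group, and the artificial difference is zero.

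**The case against.** The by-visit table is already limited to Week 8, so a reader who infers that ADA incidence in general depends on response goes too far. The problem is confined to the uncapped summaries.

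A reader might also infer that subjects whose ADA ended their response by Week 8 go unobserved. They are sampled at Weeks 2, 4 and 8 like everyone else; what is missed is ADA first detectable after they leave. Nor does sampling stop as soon as response is lost, since exit takes two consecutive collections. Protocol Appendix 3 also allows unscheduled ADA samples, and sampling beyond planned follow-up on emerging results. That allowance stands, but it is discretionary and names no population or visit, so it does not equalise follow-up.

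The correlation is exploratory, no variables are fixed for it, and the visible text of SAP 6.6 does not describe it; redacted text might. It is a risk, not a demonstrated bias. The study tests no hypotheses, cohorts have 6 active subjects, and individual listings will show when each positive occurred. All of this limits the consequence without supplying the missing window.

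The denominator wording is open too. If it means subjects with a positive result, the percentages are shares among positives, and step 3 describes the counts behind them instead. Follow-up length still decides who is counted.

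**Conclusion.** The point holds for the ADA-type table and the transient/persistent summary in Parts B–D. Planned observation ranges from 3 to 8 post-baseline samples according to HBsAg response, and SAP 6.6.2 has no rule for it. The size is uncertain: 5% against about 10–24% rests on the assumed rates above, on equal true risk, on an all-tested denominator and on full follow-up of the longer group. In a single cohort that is about one subject or fewer. The sample counts and the persistence spans do not depend on assumed rates.

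Two larger claims are not supported. A reader might extend a constant risk over five 8-week periods and get 1 − 0.95⁵ = 23% by Week 40. That needs an unchanging hazard for 40 weeks after one dose, which nothing in the documents supports. A reader might also infer that residual drug hides ADA, since about half the terminal-phase level is predicted to remain at Week 8. The documents give no assay drug tolerance, and the prediction comes from a linear model scaled from monkeys, so masking cannot be judged from them.

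This should be settled before database lock. It does not touch the primary safety endpoints.

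**What to change.** In SAP 6.6.2, for Parts B–D:

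1. Derive treatment-emergent, induced, boosted and unaffected ADA from samples through the Week 8 analysis window for all subjects. State the denominator as subjects with at least one post-baseline ADA result, which also settles the ambiguous base.
2. Use the same window for any ADA–efficacy correlation.
3. Report ADA from extended follow-up, and the transient/persistent classification that needs it, in a separate table whose denominator is the subjects sampled there.

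This matches the SAP's own practice. SAP 6.7.1 stops HBsAg loss, HBeAg loss and both seroconversion variables at Week 8, and SAP 6.8.1 cut the treatment-emergent period there to keep reporting consistent across cohorts.

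The cost is SAP wording and one extra table, with no new samples. The downside is that late positives leave the main table, so the separate table should be cross-referenced beside it.
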